5.3.2 Health care resource utilisation

Health care resource utilisation will be evaluated within 12 months before cohort entry but not including the index date. The variables listed in [Table 7](#) will be used to capture the utilisation of health care resources. Additional details on the definition of the variables in each data source are described in Section [9.2](#).

Table 7 Health care resource utilisation variables

Health care resource parameter	Definition and categories	Medications included
All dispensings	Number of dispensings for all medications; ordinal variable with 0, 1-9, 10-19, 20 or more	All medications included in Annex Table 1-6
Dispensings for respiratory medications ¹	Number of dispensings for respiratory medications; ordinal variable with 0, 1-4, 5-9, 10 or more	All medications included in the section on respiratory medications in Annex Table 1-6
Dispensings for systemic glucocorticosteroids	Number of dispensings for systemic glucocorticosteroids; ordinal variable with 0, 1-4, 5-9, 10 or more	ATC code H02AB
Dispensings for LABAs	Number of dispensings for LABAs; ordinal variable with 0, 1-4, 5-9, 10 or more	ATC codes R03AC012 (salmeterol) and R03AC013 (formoterol)
Hospitalisations	Number of hospitalisations for any cause; ordinal variable with 0, 1, 2, 3-4, 5 or more	To be determined by each data source
Hospitalisations for COPD	Number of hospitalisations with a primary discharge diagnosis of COPD; ordinal variable with 0, 1, 2, 3-4, 5 or more	ICD-10 codes for COPD: J41-J44, or as defined in Section 5.1 for each data source, but limited to inpatient codes
Hospitalisations for asthma	Number of hospitalisations with a primary discharge diagnosis of asthma; ordinal variable with 0, 1, 2, 3-4, 5 or more	ICD-10 codes for asthma: J45, J46, or as defined in Section 5.1 for each data source, but limited to inpatient codes

ATC = Anatomical Therapeutic Chemical; COPD = Chronic Obstructive Pulmonary Disease; ICD-10 = *International Statistical Classification of Diseases and Related Health Problems, 10th Revision*; LABA = Long-Acting Beta2-Agonist.

¹ Study medications will be counted (e.g., when describing the olodaterol cohort, the dispensings of indacaterol will be counted and vice versa).

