Very severe	Occurrence of at least one of the following events in the 12 months before the index date unless another time period is specified: 
 • Dispensed oxygen therapy^{1,2} • Dispensed nebuliser therapy^{1,2} • Diagnosis of emphysema at any time before the index date¹

COPD = Chronic Obstructive Pulmonary Disease.

- 1 Severity criteria also included in definition from Curkendall et al., 2006 [[P07-09136](#)].
- 2 Severity criteria also included in definition from Soriano et al., 2001 [[R08-1492](#)].
- 3 Severity criteria modified to align with the Global Initiative for Chronic Obstructive Lung Disease (GOLD) 2016 definition for severity categories C and D [[P16-00121](#)]. If two or more of these criteria occur within a 21-day time period, they will be considered part of the same exacerbation episode and counted only once. If one or more of these criteria occur within a 21-day period of a hospitalisation for COPD, this will be considered part of the same “COPD exacerbation with hospitalisation” episode.

Sources: modified from Verhamme et al., 2012 [[P11-13226](#)]; Soriano et al., 2001 [[R08-1492](#)]; Curkendall et al., 2006 [[P07-09136](#)]; and GOLD, 2016 [[P16-00121](#)].

Because data on hospitalisations are not available in the IMS RWE LPD database, COPD severity will not be described in this database.

The proposed operational definitions to be applied when assessing the severity of COPD are as follows:

- Same-class “drugs for obstructive airways disease”: medications listed in [Annex Table 1-6](#) will be identified through prescriptions/dispensings for the list of medications of interest recorded in the database within 12 months before or on the index date and classified into one of the following drug classes:
 - Bronchodilators: inhaled short-acting muscarinic antagonists (SAMAs), inhaled LAMAs, inhaled short-acting beta2-agonists (SABAs), inhaled LABAs, and fixed combinations of SABAs and SAMAs
 - Inhaled glucocorticosteroids: ICS alone, fixed combinations of SABAs and ICSs, and fixed combinations of LABAs and ICSs
 - Systemic glucocorticosteroids
 - Systemic beta2-agonists
 - Xanthines
 - Roflumilast
- Hospitalisation for COPD exacerbation: an inpatient (primary or secondary discharge) code for COPD (ICD-10 codes: J41-J44), acute bronchitis (ICD-10 codes: J20, J21, J22, J40), or pneumonia (ICD-10 codes J09, J18) within 12 months before or on the index date.

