- At least two COPD exacerbations without hospitalisation, where COPD exacerbation is defined by any of the following: a course of antibiotics, a course of systemic glucocorticosteroids, or a diagnosis of COPD exacerbation (including COPD exacerbation diagnosis *per se*, acute bronchitis, or pneumonia) during the 12 months before or on the index date. To identify exacerbation episodes, a 21-day time period will be used [[R16-1576](#)]; consecutive prescriptions of antibiotics, systemic glucocorticosteroids, or diagnosis codes for COPD exacerbation within 21 days of the first record of each episode will be considered to be a single exacerbation. When there is a hospitalisation within 21 days of the COPD exacerbation, this will be counted as one “hospitalisation for COPD or COPD exacerbation with hospitalisation.” The number of exacerbations without hospitalisation will be further categorised into 0 to 1 or ≥ 2 .
- A course of antibiotics: all dispensings for country-specific antibiotics used to treat lower respiratory tract infections (acute bronchitis or pneumonia) during the 12 months before or on the index date will be identified (a list of Anatomical Therapeutic Chemical [ATC] codes will be developed in each data source and will include those that are specific to treat the disease in each country). A course of antibiotics will be defined as treatment involving consecutive dispensings of antibiotics with less than 7 days between the end of days of supply of one dispensing and the date of the next dispensing. The variable “second course of antibiotics” will be categorised as “no” if the patient had 0 or 1 course of antibiotics during the 12 months before or on the index date, or “yes” if the patient had at least two courses of antibiotics during the 12 months before or on the index date.
- A course of systemic glucocorticosteroids: all dispensings for country-specific systemic glucocorticosteroids used to treat COPD, such as prednisolone and prednisone, during the 12 months before or on the index date will be identified (a list of ATC codes will be developed in each data source and will include those that are specific to treat the disease

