in each country). A course of systemic glucocorticosteroids will be defined as treatment involving consecutive dispensings of systemic glucocorticosteroids with less than 7 days between the end of days of supply of one dispensing and the date of the next dispensing. The variable “second course of systemic glucocorticosteroids” will be categorised as “no” if the patient had 0 or 1 course of systemic glucocorticosteroids during the 12 months before or on the index date or “yes” if the patient had at least two courses of systemic glucocorticosteroids during the 12 months before or on the index date.

- Diagnosis of COPD exacerbation without hospitalisation: an outpatient (GP, outpatient hospital clinic, or pulmonologist) ICD-10 code or ICPC code for COPD exacerbation (ICD-10 code: J44.1; free-text search in the PHARMO-GP), acute bronchitis (ICD-10 codes: J20, J21, J22, J40; ICPC code: R78), or pneumonia (ICD-10 codes: J09-J18; ICPC code: R81) within 12 months before or on the index date.
- Oxygen therapy: a prescription or dispensing for oxygen therapy (ATC code: V03AN01) within 12 months before or on the index date.
- Nebuliser therapy (to be identified in each data source using national drug codes).
- Emphysema: an outpatient or inpatient (primary or secondary hospital discharge or outpatient hospital clinics) code for emphysema at any time before or on the index date (ICD-10: J43; free-text search in the PHARMO-GP).

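### The SAP severity rule counts an admission for any reason as a COPD exacerbation if a COPD code is listed, and its 7-day and 21-day episode rules are not reconciled

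*SAP*

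**What the plan says.** Severity is assigned in SAP 5.3.3 to new users with a COPD diagnosis. A patient who meets several categories takes the most severe. Table 8 gives two routes to Severe in the 12 months before the index date: one hospitalisation for COPD exacerbation, or at least two exacerbations without hospitalisation.

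**Inpatient route.** The operational text accepts "an inpatient (primary or secondary discharge) code for COPD (ICD-10 codes: J41-J44"). It also accepts acute bronchitis codes and "pneumonia (ICD-10 codes J09, J18").

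**Outpatient diagnosis.** The code for COPD exacerbation itself is narrower ("ICD-10 code: J44.1; free-text search in the PHARMO-GP"), alongside acute bronchitis and "pneumonia (ICD-10 codes: J09-J18; ICPC code: R81").

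**Resource use.** SAP 5.3.2, Table 7, defines COPD hospitalisations as "Number of hospitalisations with a primary discharge diagnosis of COPD".

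**Drug-based exacerbations.** Table 8 counts courses of antibiotics or systemic corticosteroids. Dispensings belong to one course if there are "less than 7 days between the end of days of supply of one dispensing and the date of the next dispensing". Table 8, footnote 3, merges criteria that fall within 21 days of each other. The operational bullet words the merge differently: it refers to consecutive prescriptions, and those "within 21 days of the first record of each episode will be considered to be a single exacerbation".

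**The concern.** Three rules in SAP 5.3.3 do not fit together.

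- The inpatient rule calls an admission an exacerbation without requiring an exacerbation code, a primary position or a respiratory reason for admission. A planned operation in a patient with COPD listed second qualifies.
- The inpatient pneumonia list is two codes where every other list is a range.
- The course rule and the 21-day rule use different units, and the text does not say which is applied first.

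Describing new users of olodaterol is a primary objective, and severity has its own output, Shell Table 9. Each research centre programs its own analysis (SAP section 7), so two centres could both follow the text and count differently. Off-label prevalence does not depend on severity and is not at stake.

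**Working it through.** The documents state no expected share of Severe patients, so there is no figure to reproduce. The check compares the rules and then applies the two episode rules to example dispensing patterns.

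**1. Inpatient COPD codes**

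| Place | What counts | Position |
|---|---|---|
| SAP 5.3.3, inpatient exacerbation | J41-J44 | primary or secondary |
| SAP 5.3.3, outpatient exacerbation | J44.1 | not specified |
| SAP Table 7, COPD hospitalisations | J41-J44 | primary only |
| Protocol 9.3.3.4, hospitalisation for COPD | J40-J44 | primary or secondary |

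J44.1 lies within J41-J44, and primary position lies within primary or secondary. Replacing the inpatient rule by either narrower rule can only remove patients from the COPD-code part of the criterion. A patient can have no COPD hospitalisation in Table 7 and still be Severe through a hospitalisation for COPD exacerbation.

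The size cannot be derived. Suppose a share q of otherwise Mild or Moderate patients is admitted for another reason in the year, and COPD is coded as secondary in a share s of them. Then q × s of them move up, relative to a primary-position rule. Assuming q = 5% to 30% and s = 30% to 90%, the result runs from 0.05 × 0.30 = 1.5% to 0.30 × 0.90 = 27%. Both inputs are assumptions, so this range shows how little is known and is not an estimate.

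**2. Where it applies**

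- France: severity is not described (SAP 5.3.3).
- PHARMO: Protocol Table 8 describes the hospital records as main diagnoses. If that still holds, secondary codes hardly enter.
- Denmark: SAP Table 2 shows no GP diagnoses, so COPD is identified from hospital inpatient or outpatient codes. A Danish patient whose COPD code was recorded at any admission in the 12 months before the index date cannot be Mild or Moderate.

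**3. Inpatient pneumonia**

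The inpatient list is J09 and J18. The outpatient list in SAP 5.3.3, SAP Table 9 and the inpatient definition in Protocol 9.3.3.4 all use J09-J18. Read literally, an admission coded only J10 to J17 does not count. This lowers the number meeting the criterion.

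**4. Episode rules**

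Course rule: a new course starts if the gap from end of supply to the next dispensing is 7 days or more. 21-day rule: a new episode starts if a record falls more than 21 days after the first record of the current episode. For 30-day fills without gaps, dispensings fall on days 0, 30, ..., 360, which is 13 dispensings. Every gap from end of supply is 0, so there is 1 course. Each dispensing is 30 days after the previous one, and 30 > 21, so the 21-day rule applied to single dispensings gives 13 episodes.

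| Pattern | Dispensings | Courses | 21 days on course starts | 21 days on single dispensings |
|---|---|---|---|---|
| 30-day fills, continuous for 365 days | 13 | 1 | 1 | 13 |
| 90-day fills, continuous for 365 days | 5 | 1 | 1 | 5 |
| 14-day fills, continuous for 365 days | 27 | 1 | 1 | 14 |
| 30-day fills every 36 days (gap 6) | 11 | 1 | 1 | 11 |
| 30-day fills every 37 days (gap 7) | 10 | 10 | 10 | 10 |
| Two 30-day fills back to back | 2 | 1 | 1 | 2 |
| Two 5-day fills 15 days apart | 2 | 2 | 1 | 1 |

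Uninterrupted supply stays at 1, below the threshold of 2, whenever the merge acts on course starts. It reaches 2 or more in the continuous year-long patterns, and with two back-to-back 30-day fills, only if the merge acts on single dispensings and restarts after day 21.

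**The case against.** **The any-position rule comes from the protocol.** Protocol 9.3.3.4 already accepted primary or secondary COPD codes for severity, and Protocol 9.3.3.7 already used primary only for resource use. These are two variables with two purposes, and the protocol says that severity rests on proxies. This stands, and it weakens the Table 7 comparison as evidence of a slip. But the protocol called the event a hospitalisation for COPD. The SAP renamed it an exacerbation, in a revision meant to bring the algorithm closer to GOLD 2016, and did not tighten the codes.

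**Much of it is reported anyway.** SAP 7.1.3 shows the criteria within each severity category, and Shell Table 4.3 shows primary-diagnosis COPD admissions for COPD patients aged 40 or older. A reader could compare the two, though severity includes the index date and Table 7 excludes it. The comparison would not change how patients are classified.

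**Stronger readings.** A reader might infer that the SAP turns continuous steroid or antibiotic supply into repeated exacerbations. The documents do not support that: Table 8 counts courses, the course rule makes continuous supply one course, and footnote 3 can only merge. The figure of 13 needs one sentence on prescriptions to override all of these. A reader might also put a multiple on the excess in Severe. No document gives an admission rate or a secondary-coding rate. Meeting the criterion also differs from moving into Severe: some patients are already Severe by the other route, and emphysema, oxygen or nebuliser use places others in Very severe.

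**Conclusion.** The point holds as an inconsistency in definitions that can misclassify patients if followed literally. The inpatient COPD-code rule is broader than its label. Compared with the J44.1 rule or the primary-only count it can only add patients to the criterion. The direction is certain for that part; the size is unknown. The effect may fall mainly on Denmark, provided PHARMO still holds main diagnoses only. The short pneumonia list works in the opposite direction, so the net effect on Severe cannot be stated.

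The episode rules are ambiguous rather than inflating: the same patient can be counted as 1 or 13, depending on the unit chosen, and Table 8 with its footnote favours 1. SAP 5.3.3 allows adaptation by data source in Section 9.2, which is not in the text available for this review and may already settle some of this.

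**What to change.** 1. For classification, count an inpatient exacerbation when COPD (J41-J44) is the primary diagnosis, when J44.1 appears in any position, or when acute bronchitis or pneumonia is primary with COPD secondary. Apply this where the data source records position; where it does not, state in the source-specific definitions what is used instead.
2. Show the any-position figure as a second row in Shell Table 9.
3. Change the inpatient pneumonia codes from J09, J18 to J09-J18.
4. State that courses are formed first by the 7-day rule, and that the 21-day merge then acts on course start dates.

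The cost is SAP wording and programming, with no new data. The downside is that true exacerbations coded only as a secondary COPD diagnosis are missed by the classification; the second row shows how many patients could be affected.

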  - Inhaled short-acting muscarinic antagonists (SAMAs)
  - Inhaled long-acting muscarinic antagonists (LAMAs)

- Inhaled short-acting beta2-agonists (SABAs)
- Inhaled LABAs
- Inhaled glucocorticosteroids (ICSs)
- Fixed combinations of SABAs and SAMAs
- Fixed combinations of SABAs and ICSs
- Fixed combinations of LABAs and ICSs
- Systemic glucocorticosteroids
- Systemic beta2-agonists
- Xanthines
- Roflumilast
- Hospitalisation for COPD
  - Primary or secondary hospital discharge diagnosis for COPD
  - ICD-10 codes: J40-J44; ICD-9 codes: 491, 492, 496
- Recorded diagnosis of pneumonia
  - Primary or secondary hospital discharge diagnosis for pneumonia
  - ICD-10 codes J09-J18; ICD-9 codes: 480-486
- Third course of antibiotics for respiratory tract infections
  - A course with antibiotic is defined as that involving consecutive dispensings of antibiotics with less than 7 days between the end of days of supply of one dispensing and the date of the next dispensing
  - ATC codes for antibiotics: J01 (antibacterials for systemic use)
- Second course of systemic glucocorticosteroids for the treatment of COPD exacerbation
  - A course with systemic corticosteroids is defined as that involving consecutive dispensings with less than 7 days between the end of days of supply of one dispensing and the date of the next dispensing.
  - ATC codes for systemic glucocorticosteroids: H02AB
- Oxygen therapy, ATC code: V03AN01
- Nebuliser therapy (to be identified in each database using national drug codes)
- Primary or secondary hospital outpatient or inpatient discharge diagnosis of emphysema at any time before the index date
  - ICD-10 code: J43; ICD-9 code: 492

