5.3.4 Respiratory comorbidity and allergies

Respiratory comorbidities other than COPD or asthma will be conditions recorded at any time before or up to 30 days after index date and will be ascertained using the diseases and codes listed in [Table 9](#). These will be described for the purpose of characterising the study population overall and the subgroup of patients classified as potential off-label users, but do not constitute “suspected off-label indications.”

Table 9 Respiratory comorbidity and allergies

Disease description ¹	ICD-10 code	ICPC code
Pneumonia	J09-J18	R81
Allergic rhinitis	J30	R97
Bronchiectasis	J47	—
Lung diseases due to external agents	J60-J69	—
Acute bronchitis or bronchiolitis ²	J20, J21, J22, J40	R78
Other respiratory conditions	J80-J99	R99

COPD = Chronic Obstructive Pulmonary Disease; ICD-10 = *International Statistical Classification of Diseases and Related Health Problems, 10th Revision*; ICPC = *International Classification of Primary Care*.

¹ Other respiratory comorbidities of interest may be described depending on data availability.

² The use of ICD-10 code J40 “Bronchitis, not specified as acute or chronic” will be assessed in the data source-specific definitions.

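### SAP 5.3.3 gives the inpatient pneumonia codes as J09 and J18 where the other lists have J09-J18, so the hospitalised-exacerbation count can only be too low

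*SAP*

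**What the plan says.** In SAP 5.3.3, Table 8 makes one hospitalisation for COPD exacerbation in the 12 months before the index date sufficient for Severe. The operational definition below the table accepts three groups of inpatient codes, whether primary or secondary: those for COPD (J41-J44), those for acute bronchitis (J20 to J22 and J40), and a third group given as "pneumonia (ICD-10 codes J09, J18".

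For exacerbations managed outside hospital, the same section uses "pneumonia (ICD-10 codes: J09-J18; ICPC code: R81) within 12 months before or on the index date". Two or more of these are needed for Severe.

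SAP Table 9 (5.3.4), which describes respiratory comorbidity, has "Pneumonia J09-J18 R81". Protocol 9.3.3.4, where a hospital discharge diagnosis of pneumonia was a Severe criterion in its own right, has "ICD-10 codes J09-J18; ICD-9 codes: 480-486".

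SAP Section 4 (item 3) explains the revised severity definition as an update towards GOLD 2016. It does not mention narrowing the pneumonia codes. SAP 5.3.3 also says that the definitions will be adapted to each data source and refers to Section 9.2 for the details.

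**The concern.** This is an operational code list. Under SAP 7, each research centre runs its own analysis from the SAP. A centre that reads the comma literally will program two pneumonia categories, and a centre that reads a range will program ten. SAP 7.1.3 reports both the severity categories and the frequency of each criterion within them, so the difference would show in reported tables. PHARMO and Denmark could then differ for a reason unrelated to their patients.

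Severity is a baseline descriptor of the users with COPD, and describing the baseline characteristics of olodaterol users is one of the two primary objectives (SAP 3). The main outcome, off-label prevalence (SAP 5.1), does not use this list.

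**Working it through.** The plan states no figure here to reproduce. The check compares code lists and then traces one admission through the rules.

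**1. Pneumonia lists side by side**

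| Place | Setting | ICD-10 codes |
|---|---|---|
| SAP 5.3.3, hospitalised exacerbation | inpatient | J09, J18 |
| SAP 5.3.3, exacerbation without hospitalisation | outpatient | J09-J18 |
| SAP Table 9 | comorbidity | J09-J18 |
| Protocol 9.3.3.4 | hospital discharge | J09-J18 |

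**2. Notation.** The inpatient definition uses a hyphen for a range (J41-J44) and commas for separate codes (J20, J21, J22, J40). By that convention the pneumonia entry means two codes. The acute bronchitis codes are the same in the inpatient and outpatient definitions; the pneumonia codes are not.

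**3. Counting categories**
- J09 to J18: 18 − 9 + 1 = 10 categories.
- Listed for inpatients: 2. Omitted: 10 − 2 = 8 (J10, J11, J12, J13, J14, J15, J16, J17).
- Omitted codes covered by the other inpatient codes (J41-J44, J20, J21, J22, J40): 0.
- Whole inpatient list as written: 4 + 4 + 2 = 10 categories. With the full range: 4 + 4 + 10 = 18.

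**4. Does another rule recover the omitted codes?** The non-hospitalised rule requires "an outpatient (GP, outpatient hospital clinic, or pulmonologist) ICD-10 code or ICPC code for COPD exacerbation" or for one of the other listed diagnoses, so it does not read inpatient records. The 21-day rule in 5.3.3 may bring in some admissions that fall close to an exacerbation recorded outside hospital.

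**5. One admission traced.** Take a patient with COPD admitted once in the 12 months, with J15 the only listed respiratory code on the stay.
- With J09-J18, the patient is at least Severe.
- With J09 and J18 only, the stay does not count. The patient is Mild or Moderate unless two non-hospitalised exacerbations, or a Very severe criterion, apply.
- In Denmark, the same J15 code from a hospital outpatient clinic would count as one of the two exacerbations needed.
- PHARMO has no hospital outpatient diagnoses (SAP Table 2). The corresponding event there is a general practitioner record coded R81, in the PHARMO-GP subset only.

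**6. Direction.** Removing codes from a qualifying list cannot add a hospitalised exacerbation. It also cannot put a patient into Severe, because anyone with a qualifying admission is already at least Severe. Any error therefore lowers the hospitalisation count and lowers Severe in favour of Mild or Moderate.

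**7. Size.** A patient is placed in the wrong category only if all of these hold:
- the stay carries a J10-J17 code;
- no stay in the window carries J09, J18, J41-J44, J20-J22 or J40;
- there are fewer than two non-hospitalised exacerbations;
- no Very severe criterion (oxygen, nebuliser, emphysema) is met.

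The documents give no admissions by code, so this number cannot be computed. The 8 of 10 counts code headings, not admissions.

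**The case against.** The strongest reply is that this is a typing slip with little effect. Several parts of that reply stand.

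- The list is headed as proposed, is to be adapted by data source, and defers to Section 9.2. That section is not in the text available for this review and may already give the full range. Only the mismatch in wording is certain; what will be programmed is not.
- Severity is assessed only in patients with recorded COPD, and a COPD code counts whether primary or secondary. Many pneumonia stays may therefore qualify anyway. This protection may be weaker in PHARMO, where Protocol Table 8 speaks of main diagnoses for admissions.
- Other routes to Severe and Very severe remain, although SAP 6.5 says oxygen therapy is not available in PHARMO.
- The protocol is the weaker comparison, because the SAP deliberately replaced the protocol's severity definition. The firmer conflict is within the SAP itself.

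None of this explains why the inpatient list should be narrower than the outpatient one.

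A reader might also infer more than the documents support:

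- *That most pneumonia admissions are lost.* The omitted headings say nothing about how often each code is used.
- *That an outpatient pneumonia outranks an admission.* One outpatient pneumonia is only half of a Severe criterion. The direct comparison on hospital-clinic ICD-10 codes applies in Denmark only.
- *That the main result is biased.* Off-label classification does not use these codes.

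**Conclusion.** The inpatient pneumonia list in SAP 5.3.3 is inconsistent with the rest of the SAP and with the protocol, and is probably a comma typed for a hyphen. As written it omits 8 of 10 categories. If it is programmed literally, the count for the hospitalisation criterion can only be too low in PHARMO and Denmark, and so can the Severe category for patients with no other route to Severe or Very severe.

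The direction is established and the size is not. The effect is probably limited, given the other qualifying codes and routes. The conclusion assumes that Section 9.2 does not already restore the range. The French database is not affected, because COPD severity is not described there, and off-label prevalence is not affected. This is a small correction to a reported descriptive table, worth making because the wording would otherwise be programmed at two sites.

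**What to change.** In the hospitalised-exacerbation definition of SAP 5.3.3, change the pneumonia codes to J09-J18, matching "pneumonia (ICD-10 codes: J09-J18; ICPC code: R81" in the outpatient definition. If the narrower list is intended, say so and give the reason in SAP Section 4.

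Confirm that the database-specific specifications in Section 9.2 and the PHARMO and Danish programs use the same range. If severity tables have already been produced from the two-code list, rerun Shell Table 9 for those two databases.

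The cost is one character in the SAP, at most a line of code in each of the two databases, and a check of the programs. No new data are needed.

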#### 9.3.2.1 On-label prescribing: indication of COPD

The indication of COPD is defined as any patient with a diagnosis of COPD, chronic bronchitis, or emphysema recorded in the database at any time before the index date or at the index date. Because COPD can occur in association with asthma, patients with a recorded diagnosis for both COPD and asthma will be considered on-label. [\[R14-0350\]](#) [\[R07-2620\]](#) [\[R08-1492\]](#).

For this study, classification of COPD status will be based on general practice diagnoses and hospital outpatient and inpatient discharge diagnoses. No validation data are available for COPD diagnoses recorded in PHARMO. In general, in Denmark and Sweden, validation has been performed for COPD diagnoses ascertained via hospital (inpatient and outpatient) diagnoses. ICD diagnoses codes for COPD have shown a good positive predictive value (PPV). In the Danish National Registers, the PPV for the hospital discharge diagnosis of COPD (ICD-10 code J44) was 92%. [\[R14-0359\]](#) In Sweden, a COPD validation study showed that the COPD diagnosis (ICD-9: 491-492, 496; ICD-10: J41-J44) recorded in the National Inpatient Registry was considered as proven in 21.7% of cases, probable in 35.5%, possible in 34.0%, uncertain in 2.1%, and unlikely in 7.0%. [\[R14-0456\]](#) The proportion of patients with asthma misclassified as having COPD was 2.1%, and the overall degree of misclassification was less than 10%. The registry was considered of acceptable validity for epidemiological research of COPD.

The ICD-10 and ICD-9 codes to identify the diagnosis of COPD are detailed in [Table 3](#). Diagnosis codes include COPD, chronic bronchitis, and emphysema.

Table 3 ICD-10 and ICD-9 diagnoses and codes to identify patients with COPD

| ICD-10 Code Description                     | ICD-10 Code | ICD-9 Code |
|---|-------------|------------|
| Chronic bronchitis                          | J41-J42     | 491        |
| Emphysema                                   | J43         | 492        |
| Other COPD                                  | J44         | 496        |
| COPD with acute lower respiratory infection | J44.0       | —          |
| COPD with acute exacerbation, unspecified   | J44.1       | —          |
| Other specified COPD                        | J44.8       | —          |
| COPD, unspecified                           | J44.9       | —          |

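### The SAP's outpatient exacerbation code list leaves out J44.0, so some clinic-coded infective flares in Denmark may be missed and the Severe COPD category may be slightly undercounted

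*SAP*

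**What the plan says.** The relevant rules are all in SAP section 5.3.3.

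- **Severe category (Table 8).** A patient is Severe with either a hospitalisation for COPD exacerbation in the 12 months before the index date, or at least two exacerbations without hospitalisation.
- **Routes to an exacerbation without hospitalisation.** An episode can be established in three ways: "a course of antibiotics, a course of systemic glucocorticosteroids, or a diagnosis of COPD exacerbation". Any one route is enough. Records within 21 days of the first record of an episode count once.
- **Outpatient diagnosis route.** The record must be "an outpatient (GP, outpatient hospital clinic, or pulmonologist) ICD-10 code or ICPC code for COPD exacerbation (ICD-10 code: J44.1; free-text search in the PHARMO-GP"). Beyond J44.1, the list adds acute bronchitis (J20, J21, J22 and J40, or R78 in ICPC) and pneumonia (J09 to J18, or R81 in ICPC).
- **Inpatient rule.** Any discharge diagnosis, whether primary or secondary, qualifies if it is a "code for COPD (ICD-10 codes: J41-J44), acute bronchitis (ICD-10 codes: J20, J21, J22, J40"). Pneumonia codes also qualify.
- **Hierarchy.** A patient who meets more than one category is placed in the more severe one.

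Protocol section 9.3.2.1, Table 3, gives J44.0 its own row, described as "COPD with acute lower respiratory infection", next to J44.1 for acute exacerbation.

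SAP Table 2 shows which sources can feed the outpatient route. Denmark has hospital outpatient clinic diagnoses and no GP diagnoses. PHARMO has GP diagnoses in a subset and no hospital outpatient diagnoses. Section 5.3.3 states that severity will not be described in the French database.

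**The concern.** The outpatient list accepts acute bronchitis and pneumonia codes that do not mention COPD. It also accepts J44.1. So the plan means an acute lower respiratory infection in a COPD patient to count as an exacerbation. The one code that names both the COPD and the infection is nevertheless absent, and no reason is given. The inpatient rule does accept it.

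There is a good reason to keep most J44 codes off an outpatient list: a routine clinic visit coded J44.9 is not a flare. That reason does not reach J44.0, whose description is of an acute event.

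What is at stake is the severity distribution of new users. It belongs to the second primary objective, the description of baseline characteristics. SAP section 7.1.3 reports both the severity categories and the criteria met within each, so a missed flare can lower the reported exacerbation criterion even where the patient's category does not change.

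**Working it through.** No figure in the plan depends on this code list, so there is nothing to reproduce. The check is a comparison of the lists, followed by an illustration of size.

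**1. Code by code**

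| Code | Outpatient rule | Inpatient rule |
|---|---|---|
| J44.1 | counts | counts |
| J20.9, J22 | counts | counts |
| J18.9 | counts | counts |
| J44.0 | does not count | counts |
| J44.8, J44.9 | does not count | counts |

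An example: two Danish patients each have two clinic visits three months apart for a chest infection, with no antibiotic or steroid dispensing, no hospitalisation and no Very severe criterion. Coded J22, the patient is Severe. Coded J44.0, the patient stays Mild or Moderate.

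**2. Which source is exposed**

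- France: severity is not described.
- PHARMO: there are no hospital outpatient diagnoses, and the GP route uses ICPC codes and free text. An ICD-10 omission has no bearing on that route.
- Denmark: hospital outpatient clinics, coded in ICD-10. The gap falls here.

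**3. What must be true for a patient to be lost**

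- The flare was seen in a hospital clinic and coded J44.0, with no other listed code.
- It had no qualifying antibiotic or systemic steroid dispensing.
- Missing it takes the patient below two episodes.
- The patient has no qualifying hospitalisation and no Very severe criterion.

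**4. Illustrative size**

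None of these inputs is in the documents; all are assumptions.

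- λ: mean number of exacerbations without hospitalisation per year, 0.6 (range 0.4 to 1.0), taken as Poisson.
- h: share of episodes seen in a hospital clinic, 0.2.
- s: share of those coded J44.0 only, 0.2 (range 0.1 to 0.3).
- u: share of those with no qualifying dispensing, 0.5 (range 0 to 1).

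The share of episodes missed is m = h·s·u. The share of patients with two or more counted episodes is P(λ) = 1 − e^(−λ)(1 + λ), and after the omission it is P(λ(1 − m)).

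| λ | h | s | u | m | P(λ) | P(λ(1 − m)) | Loss, points |
|---|---|---|---|---|---|---|---|
| 0.6 | 0.2 | 0.2 | 0 | 0 | 12.19% | 12.19% | 0 |
| 0.6 | 0.2 | 0.2 | 0.1 | 0.004 | 12.19% | 12.11% | 0.08 |
| 0.6 | 0.2 | 0.2 | 0.5 | 0.02 | 12.19% | 11.80% | 0.39 |
| 0.6 | 0.2 | 0.2 | 1 | 0.04 | 12.19% | 11.41% | 0.78 |
| 1.0 | 0.2 | 0.3 | 1 | 0.06 | 26.42% | 24.22% | 2.21 |

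The last row sets every input other than h at its least favourable value. It needs no J44.0 flare ever to be followed by a qualifying dispensing, which is hard to credit for an infective event.

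For a patient with exactly two true episodes, the chance of falling below the threshold is 1 − (1 − m)². At m = 0.02 this is 1 − 0.98² = 4.0%. With three true episodes it is 3m²(1 − m) + m³ = 0.12%.

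These figures concern the two-exacerbation criterion. The effect on the Severe category is smaller still, because patients with a qualifying hospitalisation or a Very severe criterion keep their category.

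**The case against.** The strongest case against has four parts.

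- **The dispensing routes catch most of these flares.** An antibiotic or systemic steroid course makes the episode count whatever code the clinic chose, and Denmark has pharmacy dispensing data. The antibiotic list is to be built for lower respiratory infections, which is what J44.0 describes. This stands, and it limits the size. It does not remove the gap: the diagnosis route adds episodes only where no dispensing qualifies, and there J44.0 fails while J22 succeeds.
- **Few Danish episodes carry an outpatient code at all.** SAP section 7.3 says that COPD is managed mainly in primary care, and the Danish data have no GP diagnoses. Flares seen only by a GP are untouched by this list. This stands too, and it is why h appears in the calculation.
- **The Danish list may differ.** Section 5.3.3 calls these definitions proposed, to be adapted by source in section 9.2, which is not in the supplied text. J44.0 may already be there. That is a reason to check section 9.2, not to leave the core list inconsistent.
- **The databases are analysed separately, and their severity inputs already differ.** SAP section 6.5 notes that PHARMO lacks oxygen therapy. This weakens any claim about comparability between sources, so the point does not rest on one.

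A reader might infer that whether a flare counts turns on the clinic's code alone. The alternative dispensing routes rule that out.

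**Conclusion.** The omission is real, and nothing in the supplied text explains it. Within the stated rule it can only lower the count of exacerbations without hospitalisation, and only in Denmark. It may therefore undercount Severe there.

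A reader might go further and conclude that Severe COPD is undercounted in Denmark as a matter of fact, or by many points. The documents do not support that. They give no share for J44.0, and the loss is zero if every such flare has a qualifying dispensing. The net direction for Severe is also not established, because the inpatient rule counts any secondary COPD discharge code as a hospitalisation for exacerbation, which may push the category upward.

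With a fifth of episodes seen in hospital clinics, the illustration gives a loss of about 0.4 points on the two-exacerbation criterion. Over the other assumed ranges the loss runs from 0 to 2.2 points. These values show scale and are not estimates.

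The off-label outcome is unaffected: SAP Table 5 identifies COPD by J41-J44, which includes J44.0. This is a code-list correction to a descriptive baseline variable, worth making because it costs so little.

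**What to change.** In SAP section 5.3.3, in the definition of a COPD exacerbation diagnosis without hospitalisation, change J44.1 to J44.0, J44.1. Carry the change into the Danish database-specific specification in section 9.2 if it is not already there. Leave the other codes and the 21-day rule unchanged. If the omission was deliberate, state the reason in section 5.3.3 instead.

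The cost is one code in the SAP and in the Danish program, with no extra data. The downside is that the Danish Severe percentage may rise slightly.
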